#### 4.4 Clinical Biomarker Correlations

Correlations will be performed using both Pearson and non-parametric Spearman correlations. The correlations and corresponding p-value will be presented. The correlations of primary

interest are change from baseline in ventricle volume to month 12 with change from baseline to month 12 in MoCA (and CBFS) for the Study Population.

There are three types of correlations:

- ***Correlations of change:*** Correlations between change from baseline in MRI and biomarker endpoints and change from baseline in clinical endpoints
- ***Prognostic correlations:*** Correlations between baseline values in MRI and biomarker endpoints and change from baseline in clinical endpoints
- ***Cross-sectional correlations:*** Correlations between values at each timepoint.

Endpoints include the following:

- ***MRI endpoints:*** Ventricle volume, adjusted total gray matter volume, corpus callosum thickness, corpus callosum volume, whole brain volume, white matter lesion volume, brain volume composite, and ALSP MRI Severity score
- ***Fluid biomarker endpoints:*** NfL (Serum), GFAP (Serum), GFAP (CSF), NfL (CSF), sCSF1R (CSF), sTREM2 (CSF)
- ***Clinical endpoints:*** MoCA, CBFS Total Score, CGI-S/C, CDR®+NACC-FTLD Sum-of-Boxes

Tables in the Appendix ([Section 6.3](#)) provide the set of correlations to be calculated for the key clinical, fluid biomarker and MRI endpoints provided above for two populations.

## 4.5 Safety Endpoints

Safety summaries will be performed for the Study Population and the following subgroups:

- Prodromal
- Symptomatic ALSP subjects
  - Symptomatic ALSP subjects (Prior HSCT)
  - Symptomatic ALSP subjects (Non-HSCT)

### 4.5.1 Columbia-Suicide Severity Rating Scale (C-SSRS)

The C-SSRS “Baseline/Screening” and “Since Last Visit” versions will be summarized with frequency counts (i.e., as a categorical variable) at each scheduled assessment visit, for baseline and post-baseline visits, respectively.

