The “Baseline/Screening” (lifetime and last 6 months) version, which assesses the lifetime experience of the subject with suicide events and suicidal ideation and the occurrence of suicide events or ideation within a specified time period prior to entry into the study, will be completed for all subjects at Screening/Baseline to determine eligibility. For subjects with a positive response on Question 4 or 5 of the C-SSRS at Screening/Baseline, a risk assessment should be done by a qualified healthcare professional to assess whether it is safe for the subject to participate in the study.

The “Since Last Visit” C-SSRS form will be completed at Months 6, 12, 18, 24, 30, and 36/ET. If a subject demonstrates potential suicidal ideation associated with actual intent or method or plan as indicated by “YES” answers on Question 4 or 5 of the C-SSRS, the investigator will evaluate whether a risk assessment by a qualified mental health professional (or the investigator alone if the investigator is a qualified mental health professional) is needed and whether the subject should continue in or be discontinued from the trial.

8.4.4 *COVID-19 Assessments and Testing*

COVID-19 assessments (temperature and symptom assessment) and testing will be performed per local guidelines and standard of care at the site.

If a subject develops an active COVID-19 infection (whether confirmed or suspected) during the study, the investigator must consult with the sponsor medical monitor to determine the best course of action.

8.4.5 *Pregnancy Testing*

A urine pregnancy test will be performed for women of childbearing potential at Screening/Baseline and at Months 6, 12, 18, 24, 30, and 36/ET. Female subjects of childbearing potential must have a negative urine pregnancy test at Screening/Baseline for entry into the study. If a subject becomes pregnant during the study, the investigator must consult the sponsor medical monitor to determine the best course of action.

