#### 4.1.10 Study Visit

Scheduled subject visits (i.e., Screening/Baseline, Month 6, Month 12, Month 18, Month 24, Month 30, Month 36) will be determined by the visit as specified in the eCRF. That is, scheduled visits will not be windowed and the nominal visit value will be used for analysis.

To utilize as much data as possible for analysis, unscheduled and ET visits will be mapped to a scheduled visit for analysis using windows as defined below, which are to be used for analysis purposes only. Once analysis visit windows are assigned, all visits, including unscheduled and ET visits, are eligible to be flagged as the “analyzed record” within the analysis window. As such, a subject may have more than one record for each analysis visit window. The following rule for determining which record is flagged as the “analyzed record” is as follows:

- When available, data from the scheduled visit is always used.
- If data from the scheduled visit is not available, then data from the unscheduled or ET visit closest to the scheduled visit study day for that analysis window will be used, if available.

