**Table 2. Study Visit Windows**

Analysis visit	Nominal visit	Analysis visit window (days)		
		Start	End	Target
Baseline	Baseline	-28	1	1
Month 6	Month 6	93	273	183
Month 12	Month 12	275	455	365
Month 18	Month 18	458	638	548
Month 24	Month 24	640	820	730
Month 30	Month 30	823	1003	913
Month 36	Month 36	1006	1186	1096

Unless unscheduled or early termination visits are assigned to a visit window and flagged for analysis, they will be excluded from the summary tables by visit but will be included in the listings.

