### 6.2.2 Safety Assessments

#### 6.2.2.1 Columbia-Suicide Severity Rating Scale (C-SSRS)

The C-SSRS is a semi-structured tool used to assess suicidal ideation and behavior (Posner et al, 2011). It does not use a simple numerical sum, but rather classifies individuals into different risk categories based on their highest level of ideation and presence of suicidal behavior.

At study baseline, the C-SSRS “Baseline/Screening” version is administered to assess suicidal ideation over two distinct timeframes:

- ***Lifetime Assessment:*** Subjects are asked about the presence and intensity of suicidal ideation at any point in their entire lifetime.
- ***Past 6 months:*** Subjects are also asked about the presence and intensity of suicidal ideation occurring within the past 6 months to capture more recent risk.

For subsequent study visits, the “Since Last Visit” version of the C-SSRS will be used to evaluate any new or ongoing suicidal ideation and behavior that occurred since the subject’s prior visit.

- ***Since Last Visit:*** Subjects are asked about the presence and intensity of suicidal ideation since their last study visit.

The study protocol contains additional detail about using the C-SSRS to determine subject eligibility and continuation in the study, and care for the subject.

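### SAP 4.5.1 tabulates the C-SSRS only by scheduled visit, so under SAP 4.1.10 a positive early-termination or unscheduled form can be missing from every C-SSRS table

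*SAP*

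**What the plan says.** The C-SSRS is one of two safety endpoints in Protocol 3.2.3. Protocol 8.4.3 requires a Since Last Visit form at each post-baseline visit, including ET. SAP 6.2.2.1 describes its reference period: "Subjects are asked about the presence and intensity of suicidal ideation since their last study visit".

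SAP 4.5.1 states that the C-SSRS "will be summarized with frequency counts (i.e., as a categorical variable) at each scheduled assessment visit". No any-time or worst post-baseline summary is planned there or elsewhere in the SAP.

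SAP 4.1.10 decides which record enters a by-visit table:
- "unscheduled and ET visits will be mapped to a scheduled visit for analysis using windows as defined below".
- "When available, data from the scheduled visit is always used".
- The fallback applies only when the scheduled record is absent: "If data from the scheduled visit is not available, then data from the unscheduled or ET visit closest to the scheduled visit study day" is taken.

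For ET and unscheduled records that are not assigned to a window and flagged, the note to SAP Table 2 says "they will be excluded from the summary tables by visit but will be included in the listings".

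SAP Section 2 describes ET differently. In its paragraph on the CSF sub-study, it says the data-capture system maps ET to the nearest relevant visit by days from screening, and that this is usually the following one. SAP 4.1.10 also says scheduled visits keep their eCRF label and are not windowed. The SAP does not say which rule governs an ET form.

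**The concern.** Choosing one record per window, with the scheduled one preferred, suits a scale that measures current state, because a second reading nearby adds little. The Since Last Visit C-SSRS is different. Each form asks about the period since the preceding visit, and no other form asks about that period. Dropping it from the tables drops the interval.

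Suppose the Month 12 visit is on Day 365 with no ideation, and the subject leaves with an ET visit on Day 430 and a positive answer to Question 5. Both days lie in the Month 12 window (275 to 455). Month 12 is tabulated as negative and the positive form appears only in a listing. An ET visit between Day 2 and Day 92 is in no window at all.

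What is at stake is whether the tables for a named safety endpoint report every response collected. SAP 6.2.2.1 itself says the scale classifies individuals by their highest level of ideation and by any suicidal behaviour. SAP 4.5.1 produces no such classification per individual.

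**Working it through.** The documents give no figure for forms left out of the tables, so there is none to reproduce. The check counts possible ET days.

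**Inputs from SAP Table 2** (window; target): Month 6, 93–273; 183. Month 12, 275–455; 365. Month 18, 458–638; 548. Month 24, 640–820; 730. Month 30, 823–1003; 913. Month 36, 1006–1186; 1096. Each window runs 90 days either side of its target. The visit tolerance of ±14 days is from Protocol Table 1.

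**Assumptions, not in the documents:** ET is windowed under SAP 4.1.10; all earlier scheduled visits yielded a form; scheduled visits are on target; each possible ET day counts once.

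**Base case**
1. Possible ET days, Day 2 to Day 1095: 1,094.
2. Tabulated, because the ET day is in a window before that window's scheduled visit: 6 × 90 = 540.
3. Not tabulated, because the scheduled record exists: 5 windows × 91 days (target day plus 90) = 455.
4. Not tabulated, because no window applies: Days 2–92 (91 days) plus Days 274, 456–457, 639, 821–822 and 1004–1005 (8 days) = 99.
5. Check: 540 + 455 + 99 = 1,094.
6. Share not tabulated: (455 + 99)/1,094 = 554/1,094 = 50.6%. Leaving out the five target days gives (450 + 99)/1,089 = 549/1,089 = 50.4%.

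**Varying the assumptions**

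| Case | Not tabulated / possible ET days | Share |
|---|---|---|
| Visits 14 days late | (5 × 77 + 99)/1,108 = 484/1,108 | 43.7% |
| Visits 14 days early | (5 × 105 + 99)/1,080 = 624/1,080 | 57.8% |
| Follow-up to Month 24 only | (3 × 91 + 95)/728 = 368/728 | 50.5% |
| Scheduled form in the window always missed | 99/1,094 | 9.0% |
| ET labelled as the next scheduled visit | 0/1,094 | 0% |

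The wording in SAP Section 2 does not settle the matter. Day 430 is 430 − 365 = 65 days from the Month 12 target and 548 − 430 = 118 days from Month 18. Mapping to the nearest visit gives Month 12 and the same collision; mapping to the next visit gives Month 18 and no loss.

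**Recall time.** Many affected ET days fall soon after a completed visit. Three between-visit intervals have 181 possible ET days, of which the first 91 are affected; the other three have 182, of which the first 92 are affected. Summing the days since the last scheduled visit:
- affected: 3 × (91 × 92/2) + 3 × (92 × 93/2) = 12,558 + 12,834 = 25,392
- all: 3 × (181 × 182/2) + 3 × (182 × 183/2) = 49,413 + 49,959 = 99,372
- ratio: 25,392/99,372 = 25.6%

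So the affected forms would cover about a quarter of the recall time, not half.

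**The case against.** The strongest reply is that the ET loss may not occur. If the ET form carries the next visit's label in the data-capture system, SAP 4.1.10 uses that label and the form is tabulated. SAP 4.1.13 likewise says some out-of-window visits may already have been mapped during data collection. This stands as a condition on the size. It does not dispose of the point: SAP 4.1.10 explicitly windows ET visits for analysis, the Section 2 sentence is ambiguous, and that sentence does not cover unscheduled forms.

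There is also real mitigation. The records stay in the listings, which are readable with about 60 subjects. Adverse events are recorded through the ET visit and summarised without visit windows (SAP 4.5.3), so a suicidality event reported as an adverse event would be tabulated there. This is partial, since nothing requires every positive form to be so reported. Telephone visits replace scheduled visits at Months 18, 24 and 30, so they are not shown to be lost.

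A reader might infer three stronger things that the documents do not support.
- That half of ET forms are lost. The 50% is a share of calendar days under stated assumptions; ET timing is not given.
- That positives concentrate in the omitted forms. After a positive Question 4 or 5, Protocol 8.4.3 has the investigator consider "whether the subject should continue in or be discontinued from the trial", but no rate of such exits is given, and the exit route the SAP singles out (Section 1) is enrolment in the Phase 2 study.
- That the external-control comparison is biased. The primary repeated-measures models in SAP 4.3.4 concern ventricle volume, MoCA and CBFS, and no C-SSRS comparison with treated subjects is described.

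**Conclusion.** The gap is real but modest. As written, the plan allows a positive Since Last Visit form to appear in no C-SSRS table, and it has no subject-level summary that would recover it. Under SAP 4.1.10 and Table 2, with earlier scheduled forms present and visits on target, about 50% of possible ET days are affected, with a range of 44% to 58% for visits 14 days late or early. The figure is 9% if the scheduled form in the window was always missed, and about 0% if ET is labelled as the next visit. Which applies cannot be determined until the two ET mapping rules are reconciled. Whether the tabulated frequency is actually understated depends on an omitted form being positive, which the documents cannot show. Even with no ET loss, by-visit counts do not say how many subjects were ever positive after baseline, so the extra summary is worth having under either mapping.

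**What to change.** In SAP 4.5.1, add a per-subject summary of the worst post-baseline C-SSRS: the highest ideation category, and any suicidal behaviour, at any time after baseline. Base it on every Since Last Visit form, including unscheduled and ET forms, regardless of the Table 2 windows. Report it for the Study Population and the SAP 4.5 subgroups, and keep the by-visit table.

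Separately, reconcile the ET mapping sentence in SAP Section 2 with SAP 4.1.10, stating whether an ET record is analysed under its data-capture label or through Table 2.

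The cost is one paragraph, one clarifying sentence and one extra table from data already collected.

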### 4.5.2 Concomitant Therapies

Concomitant therapies will be recorded and will be presented in listings. Supportive summary tables may be produced.

#### **4.5.3 Adverse Events**

AEs will be mapped to a MedDRA version 24.0 or higher. Severity will be assessed by the investigator.

The following AE summaries will be performed:

- AEs summarized by PT and SOC
- AEs summarized by PT and SOC by severity
- AEs related to study procedures summarized by PT and SOC.
- Serious AEs (SAEs) summarized by PT and SOC

#### **4.5.4 Survival**

The number and percentage of subjects who have died will be summarized.

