Subjects who, in the discretion of the investigator, may be eligible for a VGL101 clinical study may be discontinued from this study at any time. For subjects who discontinue from this study to enroll in a VGL101 clinical study, all procedures, except the MRI, blood biomarker sampling, and CSF collection (for subjects in the CSF Sub-study), will be collected once for the Early Termination (ET) Visit of this study and for the Screening or Baseline Visit of the VGL101 clinical study and will be analyzed as part of both studies. If CSF biomarker collection is not included at the Screening or Baseline Visit of the VGL101 clinical study, CSF biomarker collection will be performed at the ET Visit of this study.

Number of Subjects

Approximately 60 subjects are planned for enrollment.

The study will enroll subjects with prodromal or definitive ALSP. Prodromal ALSP is defined as ALSP that satisfies the radiologic, but not the full clinical, criteria (see [Section 5.1](#), Inclusion Criteria). At sponsor discretion, enrollment of individuals with prodromal ALSP may be discontinued.

Treatment Groups and Duration

No study intervention will be administered. Subjects will be followed for up to 24 months (subjects who complete the study before implementation of Amendment 3) or 36 months (subjects who complete the study after implementation of Amendment 3).

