7.2 Lost to Follow-up

A subject will be considered lost to follow-up if he or she repeatedly fails to return for scheduled visits and is unable to be contacted by the investigative site. The site must attempt to contact the subject and reschedule the missed visit as soon as possible and must counsel the subject on the importance of maintaining the assigned visit schedule and ascertain whether or not the subject wishes to and/or should continue in the study.

Before a subject is deemed lost to follow up, the investigator or designee must make every effort to regain contact with the subject (where possible, 3 telephone calls). These contact attempts should be documented in the subject's medical record. Subjects who continue to be unreachable will be considered to have withdrawn from the study.

Attempts will be made to determine the survival status (alive or deceased) of any subjects who fail to return for their study visit or who discontinue from the study before completing the 24-month (subjects who withdraw from the study before implementation of Amendment 3) or 36-month (subjects who withdraw from the study after implementation of Amendment 3) observation period. Study staff will contact the subject or the subject's study partner by telephone to determine survival status 24 or 36 months, respectively, after the date of the subject's Screening Visit or at the end of the study, whichever occurs sooner.

Discontinuation of specific sites or of the study as a whole is described in Appendix 1 ([Section 10.1.6](#)).

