8.6 Survival Assessment

Attempts will be made to determine the survival status (alive or deceased) of any subject who fails to return for the vial visit or who discontinues from the study before completing the 24-month (subjects who withdraw from the study before implementation of Amendment 3) or 36-month (subjects who withdraw from the study after implementation of Amendment 3) observation period. Study staff will contact the subject or the subject's study partner by telephone to determine survival status 36 months after the date of the subject's Screening Visit or at the end of the study, whichever occurs sooner.

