Subjects who, in the discretion of the investigator, may be eligible for an iluzanebart (VGL101) clinical study may be discontinued from this study at any time. For subjects who discontinue from this study to enroll in an iluzanebart (VGL101) clinical study, all procedures, except the Magnetic Resonance Imaging (MRI), blood biomarker sampling, and CSF collection (for subjects in the CSF Biomarker sub-study), which will be collected once for the ET Visit of this study and for the Screening or Baseline Visit of the iluzanebart (VGL101) clinical study and will be analyzed as part of both studies. If CSF biomarker collection is not included at the Screening or Baseline Visit of the iluzanebart (VGL101) clinical study, CSF biomarker collection will be performed at the ET Visit of this study.

The study schema is presented below, and the Schedule of Assessments is provided in the Appendix (Section 6.1).

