#### **4.1.7 Descriptive Statistics**

Descriptive statistics will be used to summarize data from this study.

In general, continuous data will be summarized with number of subjects (N), number of observations (n), arithmetic mean, standard deviation (SD), median, minimum, and maximum. For fluid biomarker variables, percent coefficient of variation (%CV), geometric mean, and percent geometric coefficient of variation (%gCV) will also be presented.

The minimum and maximum will be reported to the same number of decimal places as the raw data recorded in the database. The mean, median, lower quartile and upper quartile will be reported to one more decimal place, and the SD (and the standard error [SE], if applicable) will be reported to two more decimal places than the raw data recorded in the database. In general, the maximum number of decimal places reported shall be four for any summary statistic.

Categorical data will be summarized in terms of the number of subjects providing data at the relevant time point (n) and percentages. Percentages will be presented to one decimal place. Percentages will not be presented for zero counts. Percentages will be calculated using n (the number of observations with non-missing values) as the denominator. A missing category shall be included only for categorical variables where no data is available. The missing category will be omitted if there were no missing values for that variable.

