#### **6.2.2.4 Survival Assessment**

Attempts will be made to determine the survival status (alive or deceased) of any subject who is lost to follow-up or who discontinues from the study before completing the 24-month (subjects who withdraw from the study before implementation of Amendment 3) or 36-month (subjects who withdraw from the study after implementation of Amendment 3) observation period. Study staff will contact the subject or the subject's caregiver by telephone to determine survival status 36 months after the date of the subject's Screening Visit or at the end of the study, whichever occurs sooner.

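### Deaths are reported as one crude percentage over unequal follow-up, so the figure estimates mortality at no stated time; add Kaplan-Meier estimates and a transfer rule

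*SAP*

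**What the plan says.** SAP 4.5.4 is one sentence: "The number and percentage of subjects who have died will be summarized". SAP 4.5 sets where it applies: "Safety summaries will be performed for the Study Population and the following subgroups", namely prodromal and symptomatic, the latter split by prior HSCT. Neither document gives a time point, person-time, censoring rule, confidence interval or Kaplan-Meier estimate for survival. The general rule in SAP 4.1.7 is "Percentages will be calculated using n (the number of observations with non-missing values) as the denominator".

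Follow-up is unequal:
- Protocol 1.1: "Subjects will be followed for up to 24 months (subjects who complete the study before implementation of Amendment 3) or 36 months", the latter for those completing after Amendment 3.
- SAP 2: a subject who may be eligible for a VGL101 study "may be discontinued from this study at any time".
- SAP 4.1.2: a second interim analysis, with a freeze on or around 11 April 2025.

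Vital status (alive or deceased) is sought by telephone for subjects who discontinue or do not return. Protocol 7.2 has staff call "to determine survival status 24 or 36 months, respectively, after the date of the" Screening Visit, or at study end if sooner; Protocol Table 1 and SAP Figure 1 agree. Protocol 8.6 has them "determine survival status 36 months after the date of the" Screening Visit, and SAP 6.2.2.4 likewise "to determine survival status 36 months after the date of the" Screening Visit. Both keep the study-end limit but drop the 24-month option, although each names the 24-month group one sentence earlier.

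**The concern.** A percentage of deaths can be read as mortality only when everyone has been at risk for the same time, or the time is stated. Neither holds here. Two subgroups with the same death rate but different entry dates or transfer rates would show different percentages.

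This matters because Protocol 2.2.1 describes ALSP as fatal, the third objective is to lay the foundation for an external control arm, and SAP 4.1.1 times the freeze to the Phase 2 freeze so that the studies can be integrated. A death percentage with no time attached cannot serve that purpose. In addition, the survival contact continues after discontinuation, and no rule separates deaths after transfer to VGL101 from deaths in the untreated course.

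**Working it through.** The plan states no mortality rate, expected number of deaths or survival precision, so there is no figure to reproduce. The check uses the documents' dates and then an illustration.

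**Step 1. Follow-up possible at the freeze (11 April 2025; month = 30.4375 days).**
- Entry on the original protocol date, 14 May 2021 (SAP Table 1): 46.9 months, capped at 36 by design.
- Entry after the first interim cutoff, 22 September 2023 (SAP 4.1.1): at most 18.6 months. If the 42 subjects in that analysis were all those then enrolled, this is 60 - 42 = 18 of 60, or 30%.
- 36 months is possible only for entry by about 11 April 2022, and 24 months only by about 11 April 2023.

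**Step 2. Assumptions, none from the documents.** Constant hazard; 36-month mortality M36 between 5% and 35%; 42 entries spread evenly up to 22 September 2023 and 18 after it; first entry 14 May or 1 October 2021; last entry 1 April or 31 December 2024. These patterns give 19-27% of subjects with 36 months, 54-57% with 24 months, and median follow-up of 25-27 months. The 36-month shares are upper limits, because subjects who completed at Month 24 before Amendment 3 are not removed.

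**Step 3. Crude percentage, all 60 in the denominator, status known to the freeze.** With λ = -ln(1 - M36)/36 and t_i = min(months from entry to freeze, 36), crude = mean of 1 - exp(-λ t_i).

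| True M36 | True 24-month | Crude |
|---|---|---|
| 5% | 3.4% | 3.4-3.6% |
| 10% | 6.8% | 6.8-7.3% |
| 20% | 13.8% | 13.7-14.8% |
| 30% | 21.2% | 20.8-22.5% |
| 35% | 25.0% | 24.4-26.4% |

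The crude figure is about 25-32% below M36 in relative terms, but close to 24-month mortality. If 20% or 40% of subjects leave early and no later status is obtained, a true 20% shows as 12.3-13.4% or 11.0-11.9%.

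**Step 4. Non-missing denominator (SAP 4.1.7).** Take M36 = 20%, with entry from 1 October 2021 to 31 December 2024. Expected deaths are 60 × 0.137 = 8.2.
- If status is recorded only for deaths and for survivors reaching Month 24, about 26.6 survivors count: 8.2/(8.2 + 26.6) = 23.6%.
- If it is recorded only for deaths and for survivors reaching Month 36, 60 × 0.187 × 0.80 = 9.0 survivors count: 8.2/(8.2 + 9.0) = 48% (47.8% unrounded).

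Over the four entry patterns the ranges are 23-25% and 39-49%. The same deaths thus give about 14%, 24% or 48%, depending on a denominator that 4.5.4 does not define.

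**Step 5. Would Kaplan-Meier help?** Simulation: 4,000 runs, N = 60, the entry pattern of Step 4.

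| True M36 | Mean crude | Mean KM at 36 months | SD of KM | Mean deaths |
|---|---|---|---|---|
| 10% | 6.8% | 10.1% | 5.4 points | 4.1 |
| 20% | 13.6% | 19.9% | 7.0 points | 8.2 |
| 30% | 20.7% | 29.9% | 8.2 points | 12.4 |

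Kaplan-Meier recovers the 36-month value, but imprecisely.

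**The case against.** The best defence is that this is a safety summary and nothing more. Survival is not among the endpoints in Protocol 3.2 (the safety endpoints are adverse events and the C-SSRS). The study is exploratory, and the SAP's primary models concern ventricle volume, MoCA and CBFS. Neither document plans a mortality comparison with Phase 2. A count of deaths to date is accurate as a count, and 4.5.4 does not call it a 36-month rate. All of this stands and limits the weight of the point. It does not rescue the percentage, which is still set side by side for subgroups with different exposure.

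The telephone contact also answers part of the early-exit problem, since status is sought after discontinuation. It does not remove truncation at the interim freeze, nor does it say how time after transfer to VGL101 is treated. The contact-timing conflict is real but minor, because both versions are limited by study end.

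A reader might infer that mortality is simply understated, and by a wide margin. Protocol 2.2.1 gives a mean of 6-8 years to death. Applying that mean m from enrolment, with follow-up uniform over 0.5-3 years, gives crude 1 - m(e^(-0.5/m) - e^(-3/m))/2.5 = 24.8%, 21.7% and 19.3% for m = 6, 7 and 8. The 36-month values, 1 - e^(-3/m), are 39.3%, 34.9% and 31.3%. The documents do not support that reading:
- The 6-8 years runs from symptom onset, not enrolment, and the cohort includes prodromal subjects.
- The follow-up distribution has no source.
- On the same model, 24-month mortality is 28.3%, 24.9% and 22.1%, only about 3 points above the crude figure.
- Step 4 shows that the error can go the other way.

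**Conclusion.** The concern holds as one of interpretability, not of a known bias. The planned percentage mixes different times at risk, has no stated time point and no survival-specific denominator, and says nothing about transfers. It therefore cannot be read as 24- or 36-month mortality, compared between subgroups, or carried into an external control. Its error against 36-month mortality may have either sign. For a true 20%, the illustrations run from about 11% (40% early exit with no later status) to 49% (only Month 36 survivors counted). These figures rest on a constant hazard, assumed entry dates and an assumed mortality, and show sensitivity only. The point is secondary, since survival is not a protocol endpoint and deaths may be few, but it bears on the external-control objective.

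**What to change.** In SAP 4.5.4:
- Keep the crude count and define its denominator.
- Add Kaplan-Meier survival from Screening/Baseline for the Study Population, with 12-, 24- and 36-month estimates, 95% confidence intervals and numbers at risk. Show subgroups descriptively where numbers allow.
- Censor at the last known-alive date. For the natural-history estimate also censor at entry into a VGL101 study, with a sensitivity analysis that does not censor at transfer.

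In data collection, record the date of death or the last known-alive date at the survival contact. The documents specify only alive or deceased there, and adverse event recording under Protocol 8.4.1 stops at the final or ET visit, so a later death may have no date. Reconcile the contact timing between Protocol 7.2, Table 1 and SAP Figure 1 (24 or 36 months) and Protocol 8.6 and SAP 6.2.2.4 (36 months).

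The cost is one table, one figure, a date field to confirm and a wording correction. There are two statistical limits. Estimates at 36 months will be imprecise, with few at risk (SD about 5-8 points overall in Step 5, before any subgrouping). Censoring at transfer may be informative, because transfer depends on the investigator's judgement of eligibility; the sensitivity analysis is there for that reason.
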